# 7. Primary Analysis

267268

269

266

263

264

265

- The primary outcome is CGM measured % time in range 70-180 mg/dL over the two randomized crossover periods.
- Summary statistics (mean  $\pm$  SD or median (quartiles)) will be reported for the CGM-measured % in range 70-180 mg/dL at baseline, over the two randomized crossover periods, and the difference between the two periods.
- A repeated measures linear regression model will be fit for CGM-measured % in range 70-180 mg/dL.
- 274 The model will include pre-randomization baseline, the two crossover periods, and will adjust for period
- and site (as random effect). Primary analysis will report the point estimate, 95% confidence interval and
- p-value for the randomized periods difference at follow-up. Inclusion of the pre-randomization baseline
- value as a third observation for each participant in the model gives a variance reduction analogous to adjusting for it as a covariate. Baseline is not modeled as a covariate in this analysis because there is no
- corresponding baseline for the second period, but only pre-randomization. The model will account for
- 280 correlated data from the same participant. Residual values will be examined for an approximate normal
- distribution. If residuals are highly skewed, then a winsorizing at 10/90th percentile or robust statistical
- method (e.g., non-parametric or MM estimation) will be used instead. It is expected that the residual values for CGM-measured % in range 70-180 mg/dL will follow an approximate normal distribution.
- If a participant has <72hr of data for one of the two cross-over periods or at baseline, then the participant and the periods with ≥72hr of data will be included in the primary analysis.

286 287

288

# 8. Analysis of the Secondary Endpoints

289290

Point estimates and confidence intervals for the treatment period differences will be presented for all secondary metrics. Models similar with the one described above will be implemented.

291292

293

[figure not shown]
## 8.1. Hierarchical Analysis

- The only hierarchical outcome in this study will be non-inferiority in CGM-measured % below 54 mg/dL.
- 296 Regression Model
- 297 A repeated measures linear regression model will be fit for CGM-measured % below 54 mg/dL. The
- 298 model will include pre-randomization baseline, the two crossover periods, and will adjust for period and

site (as random effect). Will report the point estimate, two-sided 95% confidence interval and one-sided p-value for the randomized periods difference at follow-up. Inclusion of the pre-randomization baseline value as a third observation for each participant in the model gives a variance reduction analogous to adjusting for it as a covariate. The model will account for correlated data from the same participant. Residual values will be examined for an approximate normal distribution. If residuals are highly skewed, then a winsorizing at 10/90th percentile or robust statistical method (e.g., non-parametric or MM estimation) will be used instead. Missing data will be handled as described above for the primary analyses.

# Non-inferiority

CGM-measured % below 54 mg/dL will be a non-inferiority test with limit 1%. Since non-inferiority is typically framed in terms of a one-sided test, it is worth noting that the left half of a two-sided test at alpha = 0.05 gives the same rejection region as a one-sided test at alpha = 0.025. Therefore, reporting a two-sided 95% confidence interval will provide flexibility to also test for inferiority if non-inferiority cannot be declared, or superiority if non-inferiority is declared. Note that since all tests for non-inferiority/inferiority/superiority are based on the same confidence interval, the overall type 1 error rate is maintained at 5%. The following figure shows examples of the inference to be drawn for a non-inferiority analyses based on the two-sided 95% confidence interval in various scenarios:

Difference in CGM-measured % below 54 mg/dL (MPC vs. SAP Period)

### Hierarchical Hypothesis Testing

To preserve the overall type 1 error for non-inferiority in CGM-measured % below 54 mg/dL, a hierarchical testing procedure will be used. A formal statistical assessment of non-inferiority (limit 1%)

- for time below 54 mg/dL will only be performed if the primary analysis for CGM-measured % in range
- 70-180 mg/dL described above results in a statistically significant result (p < 0.05).
- 325 If a non-significant result is encountered for CGM-measured % in range 70-180 mg/dL, then no formal
- statistical hypothesis testing for non-inferiority CGM-measured % below 54 mg/dL will be performed,
- and analysis of this variable become exploratory. As mentioned above in section 5.2.2, superiority in
- 328 CGM-measured % below 54 mg/dL is additionally listed as an exploratory outcome.
- Regardless of the results of the hierarchical testing, summary statistics appropriate to the distribution of
- 330 CGM-measured % below 54 mg/dL will be tabulated by treatment period. A two-sided 95% confidence
- interval for the treatment period and their difference will also be calculated. However, a confidence
- interval that excludes zero will not be considered a statistically significant result if for CGM-measured
- 333 % in range 70-180 mg/dL failed reach statistical significance.

### 8.2 Secondary CGM Metrics

- The analyses for the continuous CGM-measured outcomes, including missing data, will parallel those
- mentioned above for the primary outcome.
- For the secondary and binary CGM outcomes listed above, risk-adjusted percentages by treatment
- period and the difference between treatment arms will be computed from a logistic regression model [1].
- The logistic regression will adjust for the same factors mentioned above for the primary outcome (i.e.,
- 341 period, site, and baseline value).

#### 343 **8.3 HbA1c**

334335

342

- Summary statistics [mean  $\pm$  SD or median (IQR)] will be reported for the central lab HbA1c at
- randomization and 13 weeks in each treatment period.
- Lab HbA1c values at 13 weeks will be compared between the two treatment periods using a repeated
- linear model while adjusting for period and site (random effect). Inclusion of the randomization HbA1c
- value as a third observation for each participant in the model gives a variance reduction analogous to
- adjusting for it as a covariate. The model will account for correlated data from the same participant. All
- participants with at least one HbA1c lab measurement at 13 weeks in one of the two periods will be
- included in the analysis. Regression diagnostics will be employed analogous to as described in Section 7
- 352 for the primary outcome.
- For the binary HbA1c outcomes listed above, similar analyses will be done as described above for the
- binary CGM outcomes.

### 8.4. Insulin Analyses

- Summary statistics appropriate to the distribution for total daily insulin and the bolus:basal ratio will be
- given by treatment group at baseline and at 13 weeks in each one of the two crossover periods. All
- participants with at least one CFR-reported insulin metric at 13 weeks in one of the two periods will be
- included in the analysis. Regression diagnostics will be employed analogous to as described in Section 7
- 361 for the primary outcome.

362

355

### 8.5. Weight and Body Mass Index Analyses

- Summary statistics appropriate to the distribution for weight and BMI will be given by treatment group
- at baseline and 13 weeks in each one of the two crossover periods. All participants with at least one
- reported weight metric at 13 weeks in one of the two periods will be included in the analysis. Regression
- diagnostics will be employed analogous to as described in Section 7 for the primary outcome.

368

369

363

### 8.6. Questionnaires

- For each questionnaire, mean  $\pm$  SD values or percentiles appropriate to the distribution will be given by
- randomized period for the total score and each subscale at baseline and at 13 weeks in each period.
- For questionnaires administered in both randomization periods, comparisons will be made using similar
- longitudinal models as described above for the primary outcomes. Separate models will be run for the
- total score and each of the subscales listed above, and the models will adjust for baseline questionnaire
- score. A point estimate, confidence interval and p-value will be given for the treatment period difference
- 376 at 13 weeks.

377

## 9. Safety Analyses

378379

385

386

387

- All enrolled participants will be included in these analyses and all their safety events up to the second and final 13-week visit will be reported.
- The circumstances of all reportable cases of the following will be summarized and tabulated by treatment period:
- Severe hypoglycemia
  - Diabetic ketoacidosis
  - Ketone events defined as day with ketone level  $\geq 1.5$  mmol/L
  - Worsening of HbA1c from start of the period to 13 weeks by >0.5%
- Other serious adverse events (SAE) and serious adverse device events (SADE)
- Adverse device effects (ADE)
  - Unanticipated adverse device effects (UADE)
- 391 Statistical analyses to compare rates of severe hypoglycemia and rates of diabetic ketoacidosis between
- treatment arms will only be performed if there are at least 10 events after randomization. If yes, the
- numbers will be compared between the two treatment periods using a robust Poisson regression. The
- amount of follow up will be included as an offset covariate to compare the rates.
- Comparison of safety outcomes between the two treatment periods only include those events occurring
- on or after randomization until the final 13-week visit.
- The analyses for the two continuous CGM-measured outcomes will parallel those mentioned above for
- 398 the primary outcome.

399 400	The CGM metrics listed in the above efficacy section 5.2.2. also serve as safety measures if there is worsening in the intervention group.
401 402	Any pre-randomization adverse events will be tabulated separately and will include participants who were never randomized.
403	
404 405	10. Device Issues
406 407	Reported device malfunctions or other issues for each type of study device (e.g., closed loop system, CGM, blood glucose meter)
408 409 410	11. Protocol Adherence and Retention
411 412	The following tabulations and analyses will be performed by treatment period to assess protocol adherence for the study:
413 414	
 
Number of protocol and procedural deviations per participant along with the number and percentage of participants with each number of deviations
 

415	
 
Number of protocol and procedural deviations by severity with brief descriptions listed
 

416 417 418	
 
Flow chart accounting for all participants at all scheduled visits and phone contacts post treatment initiation to assess visit and phone completion rates – will include missing, in and out of window visit and phone contacts
 

419	
 
Number of and reasons for unscheduled visits and phone calls
 

420 421	
 
Number of participants who stopped treatment and reasons
 

422	12. Baseline Descriptive Statistics
423 424 425 426	Baseline demographic and clinical characteristics of the cohort of all randomized participants will be summarized in a table using summary statistics appropriate to the distribution of each variable. Will include:
427	• Age
428	• Gender
429	• Race/ethnicity
430	
 
Income, education, and/or insurance status
 

431	
 
Diabetes duration
 

432	
 
Daily SMBG at enrollment
 

433	• HbA1c

434	• BMI
435	• C-peptide
436	• Participant-reported number of SH and DKA 12 months prior to the start of the study
437 438	
439 440	13. Other Tabulations
441	Individual listings for each participant will include the following:
442	• Treatment period order, age, gender, race/ethnicity, duration, height, weight, and BMI
443 444	• Study related information (like enrollment and randomization dates, enrollment and randomization HbA1c, randomization C-peptide, status, run-in requirement)
445	
 
Previous SMBG use, non-insulin medications, devices months used and manufacturer
 

446	Past SH and DKA events
447	
 
Physical exam results
 

448	
 
Income, education, and insurance
 

449	
 
Pre-existing medical conditions other than diabetes
 

450	
 
Medication at enrollment
 

451	Baseline glucose metrics
452 453	The following tabulations and analyses will be performed by treatment period:
454	
 
Percent sensor use – overall and by month
 

455	• The daily frequency of downloaded SBGM use - overall and by month
456 457	The following tabulations and analyses will be performed for MPC period only:
458	
 
Percent time in different operational modes - overall and by month
 

459	Percent change of clinical and controller adaptation parameters throughout closed-loop use
460 461	
 
Rate of different failure events and alarms per 24 hours recorded by the system – overall and by month
 

462 463 464 465	14. Planned Interim Analyses
466	
467	No formal interim efficacy analyses are planned for this study.

The DSMB will review all cases of severe hypoglycemia and diabetic ketoacidosis irrespective of device relationship, all device related SAEs, and all UADEs at the time that they occur during the study and will review compiled safety data at periodic intervals. The DSMB can request modifications to the study protocol or suspension or outright stoppage of the study if deemed necessary.

473 474

475

476

477

478

479

481

482

483

484

- The data to be reviewed periodically by DSMB will include information regarding the following:
  - Status of randomized participants
  - Recruitment rates by month and by site
  - Baseline demographic and clinical characteristics
  - Dropped participants and reasons for discontinuing
- Protocol deviations
- Device issues
  - Scheduled and unscheduled visits and contacts
  - Frequency of CGM and system use over time and by site
  - Reportable adverse events as described in Section 10 of the protocol
  - CGM-based hypo- and hyper-glycemic events during baseline and all available post randomization data

485 486

487

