	6) Participation in another pharmaceutical or device trial at the time of enrollment or during the study
Sample Size	Up to 35 individuals randomized in the crossover trial with the goal of at least 32 completing the trial
Treatment Groups	Random assignment (1:1) to begin period 1 either with the AID study system or with SAP using home pump and then cross over to the other respective treatment in period 2
Participant Duration	6-7 months
Protocol	Screening and Enrollment
Overview/	• Informed consent will be signed, and eligibility will be assessed
Synopsis	Medical history and physical examination
	• HbA1c measurement using point-of-care device (if not available from prior 3 months)
	• Urine pregnancy test (if applicable)
	Baseline questionnaires completed
	Pilot Phase
	The Pilot Phase will include 1-2 participants at each site, using a personal Dexcom G5/6 with use on at least 11 of the prior 14 days and the investigator believes that a CGM run-in is unnecessary. The Pilot Phase is intended to (1) test the functionality of all aspects of the study System and (2) train the clinical staff on the execution of the clinical protocol, including hands-on training with the device prior to initiating the RCT Period. Screening and study system start up procedures will be the same as for the Crossover Trial. Participants will use the study system for 10-14 days. After at least 5 total participants from at least 3 different sites have completed the Pilot Phase, the data will be reviewed for preset safety criteria before proceeding to the RCT. Assuming there are no significant safety or device issues that occur, the Crossover Trial will begin.
	CGM Run-In (2-4 weeks)
	Eligible participants using a personal Dexcom G5/G6 sensor, with use on at least 11 of the prior 14 days may skip the CGM run-in unless the investigator believes that there is a need to optimize insulin pump settings prior to randomization. Participants skipping the run-in can go directly to the randomization visit.
	Eligible participants not currently using a personal Dexcom G5/G6 sensor or using a Dexcom G5/G6 sensor with readings captured on less than 11 out of the prior 14 days will initiate a CGM run-in phase with a study Dexcom G6 sensor.
	• Users of a sensor other than Dexcom G5/G6 (eg, Medtronic, Abbott) must be willing to discontinue use of that sensor for the duration of the study and users of an AID (closed loop

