control) system must be willing to discontinue its use during the study (PLGS mode can be used during the study if feasible).

Duration of the run-in will be 2-4 weeks at investigator discretion. During this time, Study Staff will review uploaded CGM data and may optimize insulin pump settings as needed by phone contact with subjects. Prior to each phone contact, the participant will be asked to upload the CGM and if possible pump data for study staff review. Successful completion of the run-in will require use of the sensor for at least 11 days during a final assessment period of 14 days.

The run-in may be extended at investigator discretion if the investigator believes that additional training is needed or the participant should have another opportunity to achieve the 11 day use criterion.

Randomized Cross-Over Trial

Eligible participants will be randomly assigned to one of two treatment groups for 13 weeks each:

- 1. Group A: study system for period 1 for 13 weeks, then SAP for period 2 for 13 weeks
- 2. Group B: SAP for period 1 for 13 weeks, then study system for Period 2 for 13 weeks

Study System Period: The participant will be trained regarding AID study system use including meal announcement, meal bolusing, correction doses, and exercise. Participants will be expected to use the study system at all times at home with the exception of times of illness.

SAP Period: During the SAP period, participants will use their own insulin pump and a study-provided Dexcom G6 sensor.

• *PLGS mode on the pump can be used if feasible but an AID system cannot be used.*

Study Flow

Period 1 will commence on the day of randomization with initiation of the study system or continued use of personal pump SAP.

[figure not shown]
Both groups will have the same contact and visit schedule in both period 1 and period 2

- Visits at 2 weeks, 6 weeks, and 13 weeks
- Phone contacts at 3 days, 4 weeks, and 9 weeks

At randomization, and at each end of period visit, central lab HbA1c measurement will be made, a pregnancy test will be performed in applicable subjects, and quality of life and treatment satisfaction questionnaires will be completed.

At the end of period 1 visit, the intervention will be switched to the study system or SAP for period 2. There will not be a washout period.

Throughout the study, the occurrence of adverse events and device issues will be solicited and recorded.

Schematic of Study Design

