25 Several clinical studies using the novel zone MPC control framework which is the basis for the proposed research shows consistently that the Artificial Pancreas (AP) is able to improve glucose 26 regulation in T1D. [name] et al. (FDA IDE G090129) published in 2013 results of a pilot clinical 27 trial conducted at Sansum Diabetes Research Institute (SDRI), evaluating individualized, fully 28 29 automated (no premeal bolus) AP using commercial devices (1). Two trials (n=22, n=17) were 30 conducted using a multi parametric formulation of MPC and an insulin-on-board algorithm. 31 Continuous glucose monitor (CGM) glucose was maintained in the near-normal range 70-180 32 mg/dL for an average of 70% of the trial time. These results showed the ability of a control 33 algorithm tailored to an individual's physiology to successfully regulate glycemia, even when faced with unannounced meals or initial hyperglycemia. We (FDA IDE G110093) studied the 34 35 safety and efficacy of a fully automated AP using zone MPC with the health monitoring system 36 (HMS) during unannounced meals and overnight and exercise periods. A fully automated closedloop AP was evaluated in 12 subjects with T1D and demonstrated 80% and 92% time in the 70-37 38 180 mg/dL range for the entire session and overnight, respectively. These results showed that the 39 combination of the zone MPC controller and the HMS hypoglycemia prevention algorithm was 40 able to safely regulate glucose in a tight range with no adverse events despite the challenges of 41 unannounced meals and moderate exercise. The zone MPC algorithm was successfully used in 42 2015 (FDA IDE G130147), when Drs. [name] and [name] AP team, Mayo Clinic and SDRI, 43 among other sites, showed in a randomized clinical trial of 32 subjects in a transitional 44 environment (such as hotel) that algorithmic adjustment of individualized insulin dosing

- 45 parameters was safe and effective for AP use (2). As part of the DP3DK094331 research project,
- the fruitful collaboration among Drs. [name] and [name] AP team, UVA, Mayo Clinic, SDRI and
- 47 other collaborators yielded a large outpatient clinical trial of the zone MPC and HMS system
- 48 (FDA IDE G150063), where 30 adult subjects each used AP at home for three months (3). This
- 49 study resulted in a statistically significant decrease in HbA1c (-0.3, 95% CI -0.5 to -0.2,
- 50 p<0.001) and hypoglycemia during the day from 5.0 to 1.9% (-3.1, 95% CI -4.1 to -2.1,

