#### **Randomized Crossover Trial**

Eligible participants will be randomly assigned to one of two treatment groups for 13 weeks each:

- 1. Group A: study system for period 1 for 13 weeks, then SAP for period 2 for 13 weeks
- 2. Group B: SAP for period 1 for 13 weeks, then study system for Period 2 for 13 weeks

Study System Period: The participant will be trained regarding AID study system use including meal announcement, meal bolusing, correction doses, and exercise. Participants will be expected to use the study system at all times at home with the exception of times of illness.

SAP Period: During the SAP period, participants will use their own insulin pump and a study-provided Dexcom G6 sensor.

• PLGS mode on the pump can be used if feasible but an AID system cannot be used.

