#### **Study Flow**

Period 1 will commence on the day of randomization with initiation of the study system or continued use of personal pump SAP.

Both groups will have the same contact and visit schedule in both period 1 and period 2

- Visits at 2 weeks, 6 weeks, and 13 weeks
- Phone contacts at 3 days, 4 weeks, and 9 weeks

At randomization, and at each end of period visit, central lab HbA1c measurement will be made, a pregnancy test will be performed in applicable subjects, and quality of life and treatment satisfaction questionnaires will be completed.

At the end of period 1 visit, the intervention will be switched to the study system or SAP for period 2. There will not be a washout period.

Throughout the study, the occurrence of adverse events and device issues will be solicited and recorded.

37 38

The following table provides an overview of the schedule of study visits, phone contacts, and key procedures.

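### HbA1c worsening is measured from the start of each period with no washout, so losing the AID benefit counts as harm on the comparator

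*SAP*

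**What the plan says.** SAP Section 9 and Protocol 12.8 use the same definition: "Worsening of HbA1c from start of the period to 13 weeks by >0.5" percentage points. It stands in a list of safety outcomes to be summarized and tabulated by treatment period. Neither document names the measurement that serves as the start value.

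The rest of the design settles it:

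- **HbA1c schedule** (SAP Study Flow; Protocol synopsis, Table 1 and 9.1): "At randomization, and at each end of period visit, central lab HbA1c measurement will be made". No other central-lab value is scheduled.
- **Washout** (Protocol synopsis, Study Flow): "There will not be a washout period".
- **Sequences** (SAP Section 1, Randomized Crossover Trial): "Group A: study system for period 1 for 13 weeks, then SAP for period 2 for 13 weeks"; "Group B: SAP for period 1 for 13 weeks, then study system for Period 2 for 13 weeks". Allocation is 1:1, so about half of all comparator periods follow AID.

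Other HbA1c analyses use a different reference. SAP Section 8.3 models 13-week HbA1c with the randomization value as a third observation. Protocol 12.4.2.2 defines the HbA1c improvement outcomes from baseline. In explaining the primary model, SAP Section 7 says there is no "corresponding baseline for the second period, but only pre-randomization". The carry-over check in SAP Section 6.2 covers the primary outcome only.

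**The concern.** For period 2 the start-of-period value is itself an outcome of the other treatment. A Group A participant whose HbA1c falls on AID and then returns on the comparator to exactly where it was before the study has not been harmed by the comparator, yet a rise of more than 0.5 points is recorded against it. Group B has no mirror image, because its AID period starts from a level reached on sensor-augmented pump therapy.

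The more effective AID is, the more worsening is charged to the comparator. SAP Section 9 plans to compare safety outcomes between the two treatment periods, so readers will set these two counts side by side. Nothing in the plan would separate true deterioration from loss of the AID effect in that table.

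**Working it through.** The documents give no expected rate for this outcome, so there is no stated figure to reproduce. The size is worked out from the protocol's own prior result.

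**Inputs**

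- AID effect on HbA1c: Protocol 1.1.1 reports a "statistically significant decrease in HbA1c (-0.3, 95% CI -0.5 to -0.2") in 30 adults over three months.
- SD of change implied by that interval: half-width / t(0.975, 29 df) × √30 = 0.15 / 2.045 × 5.477 = 0.40. The limits are rounded to one decimal, so the interval width could be 0.2 to 0.4, which gives an SD of 0.27 to 0.54.
- Randomized participants: 35 (Protocol 12.3; SAP Section 4).

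**Assumptions**

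- Changes are normally distributed with the same SD in each period.
- There is no period effect and no true mean change on the comparator.
- The AID effect is fully gained, and fully lost, within 13 weeks.

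**Formula**

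P(worsening) = 1 − Φ((0.5 − μ)/σ), where μ is the mean change from the reference value.

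**As defined, effect -0.3, SD 0.40**

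- Comparator, Group B period 1: μ = 0; (0.5 − 0)/0.40 = 1.25; P = 10.6%.
- Comparator, Group A period 2: μ = +0.3; (0.5 − 0.3)/0.40 = 0.50; P = 30.9%.
- Comparator pooled: (10.6 + 30.9)/2 = 20.7% (before rounding the inputs), about 7.2 of 35.
- AID, either sequence: μ = -0.3; (0.5 + 0.3)/0.40 = 2.00; P = 2.3%, about 0.8 of 35.
- Comparator minus AID: 20.7 − 2.3 = 18.4 points.

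**Randomization HbA1c as reference in both periods**

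- Comparator: 10.6%, about 3.7 of 35. AID: 2.3%.
- Comparator minus AID: 10.6 − 2.3 = 8.3 points.

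A simulation of 400,000 participants with three HbA1c values each gave 20.6% and 2.3% as defined, and 10.6% and 2.3% with the common reference.

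**Sensitivity**

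| AID effect | SD | Comparator, as defined | Comparator, common reference | AID (both) |
|---|---|---|---|---|
| -0.3 | 0.27 | 13.1% | 3.2% | 0.2% |
| -0.3 | 0.40 | 20.7% | 10.6% | 2.3% |
| -0.3 | 0.54 | 26.6% | 17.7% | 6.9% |
| -0.2 | 0.40 | 16.6% | 10.6% | 4.0% |
| -0.5 | 0.40 | 30.3% | 10.6% | 0.6% |
| 0 | 0.40 | 10.6% | 10.6% | 10.6% |
| +0.3 | 0.40 | 6.4% | 10.6% | 30.9% |

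If only half of a 0.3-point benefit is lost by week 13 of period 2, then μ = +0.15. With SD 0.40, Group A's comparator rate is 1 − Φ(0.875) = 19.1%, still well above the 10.6% in Group B.

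**The case against.** The strongest reply is that little depends on this line. It is one descriptive entry. Formal comparison is planned only for severe hypoglycemia and DKA, and only with at least 10 events. No stopping rule uses HbA1c worsening, and the primary and hierarchical tests are untouched. SAP Section 8.3 already gives a sound HbA1c comparison, and the listings in SAP Section 13 show treatment order. The AID count is the same under either definition, so no AID harm is hidden. With no AID effect there is no bias, and if AID raised HbA1c the distortion would run against AID. All of this stands, and it limits the consequence. It does not make the tabulated difference between treatments interpretable.

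The statement in SAP Section 7 concerns the CGM primary outcome, and for HbA1c a value at the switch does exist. That is fair: the sections differ in approach and do not formally contradict each other. The fault is that the value at the switch is a post-treatment one.

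The -0.3 is described as a decrease over three months of use, so it may not equal an AID-minus-comparator contrast. The size is therefore illustrative.

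Measuring period 2 from randomization spans about 26 weeks, and lasting deterioration from Group B's first period could be charged to AID. This is a real trade-off. But under 1:1 allocation each treatment has about half its periods at the longer interval, so the two sequences are treated alike, which the present definition does not do.

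**Conclusion.** The concern holds. The schedule and the absence of washout leave the end-of-period-1 value as the only central-lab start value for period 2. This inflates worsening on the comparator in Group A's second period whenever AID lowers HbA1c.

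At the protocol's cited effect and its implied SD, the comparator rate roughly doubles, from 10.6% to 20.7%. That is about 3.5 extra cases among 35, and more than half of the displayed 18.4-point gap comes from the definition (18.4 − 8.3 = 10.1 points). Over the SD range 0.27 to 0.54 the comparator rate is 13.1% to 26.6% as defined, against 3.2% to 17.7% with a common reference.

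The direction depends only on AID lowering HbA1c and on some of that benefit being lost after the switch. The size rests on the normal model, the derived SD, and full gain and loss of the effect within 13 weeks. The damage is confined to a descriptive safety table.

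**What to change.** In Protocol 12.8 and SAP Section 9, define worsening in both periods as the 13-week central-lab HbA1c minus the randomization central-lab HbA1c exceeding 0.5 percentage points. This agrees with the reference used in SAP Section 8.3.

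If a start-of-period version is kept, report it for period 1 only, or show it by sequence and period with a note that Group A's second period mixes deterioration with loss of the AID effect.

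The cost is one line in each document. The randomization HbA1c is already collected, so no visits, samples or data are added.
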